1.1. Background Information

With a growing aging population all over the world, healthy ageing is an important goal for public health. Dietary restriction (DR), implemented as chronic and coordinate reduced intake of all dietary constituents except vitamins and minerals, was first shown more than 80 years ago to extend lifespan in model organisms and in humans. Dietary interventions that avoid unrealistic levels of self-deprivation, and pharmacological interventions that recapture beneficial effects of DR, are therefore important goals to improve human health during aging. Despite its potential for disease prevention and treatment, prolonged fasting is difficult to implement in human subjects and may exacerbate pre-existing nutritional deficiencies, making it not feasible and/or safe for children, the elderly, frail individuals, and even most of the healthy adults. Fifteen years of extensive preclinical and clinical studies sponsored by the National Institutes of Health (NIH) and conducted at the Longevity Institute and Diabetes and Obesity Research Institute of the University of Southern California (USC) resulted in the development of a very promising dietary interventions effective in extending not only longevity but also the healthy life span: the fasting mimicking diet® (FMD).

1.2. Fasting Mimicking Diet

The fasting-mimicking diet (FMD) is a 5-day meal program to be consumed every 1 to 6 months based on an authorized healthcare professional's recommendation. It is designed to promote the body's natural ability to protect, regenerate and rejuvenate itself. In clinical studies, FMD has been shown to reduce abdominal fat and maintain healthy levels of blood glucose, C-reactive protein (CRP), and insulin-like growth factor 1 (IGF-1) (Wei et al., 2017). Well-designed clinical trials, such as the study conducted by Houston et al. utilizing an independent review board (IRB) approved protocol, have demonstrated the safety and short-term benefits of plant-based nutraceuticals and food restriction in individuals with chronic hypertension (Houston et al., 2014).

A large ongoing randomized, open-label trial aimed at evaluating the effects of two different dietary interventions, FMD and LD, on body composition and cardiovascular (CV) biomarkers in a real word population (NCT05698654) is actually ongoing. This trial started in January 2024 will enrol 501 adult subjects between the ages of 30 and 65: 167 subjects randomized to the FMD arm with a 5-day meal program once every three months for a 6-month period (arm 1); 167 subjects randomized to follow the FMD plus a Longevity Diet program (FMD+LD) for a 6-month period (arm 2); 167 randomized to the control group (arm 3) that will continue their usual diet. On 2024,410, participants were enrolled and randomly assigned to FMD, FMD + LD, or control arm. Although preliminary data demonstrated the beneficial effects of such nutritional plans on body weight, BMI, body composition, and cardiovascular (CV) biomarkers, limited data is available on the long-term effects of these powerful nutritional interventions.

2. Study Objectives/Endpoints

2.1. Objectives The objective of the study is to determine long-term trends of a 5-day FMD meal program in patients already subjected to FMD in a previous trial (NCT05698654) and that will continue an FMD-based plan to assess its long-term effect on fat mass maintenance. The secondary objectives are to determine long-term trends of a 5-day FMD meal program in patients already subjected to FMD who will continue an FMD-based plan to assess its long-term effect on the maintenance of body weight, body mass index, blood pressure, IGF-1, haemoglobin A1c, fasting glucose, LDL, total cholesterol, C-Reactive Protein, and the proportion of participants who received medications at baseline.

2.2. Endpoints

- 2.2.1. *Primary endpoint*: maintenance of at least 50% of the fat mass lost during the previous trial and measured after one follow up year on FMD every 3 months
- 2.2.2. *Secondary endpoints*: maintenance of at least 50% of one or more risk factors improvements achieved during the previous clinical trial and measured after one year of follow up FMD cycles every 3 months including improvements in: body mass, body mass index, blood pressure, IGF-1, haemoglobin A1c, fasting glucose, LDL, total cholesterol, and C-Reactive Protein. Determine long-term trends in the reduction/stabilization in the use of antihypertensive and glucose-lowering drugs or other commonly used medications.

3. Study Design

Follow up clinical trial including participants of the approved studies “*Studio degli effetti della dieta mima-digiuno e della dieta della longevità sulla composizione corporea, fattori di rischio per malattie età-correlate e marcatori dell'invecchiamento in uno studio randomizzato*” and “*Studio degli effetti della dieta mima-digiuno e della dieta della longevità sulla composizione corporea, fattori di rischio per malattie età-correlate e marcatori dell'invecchiamento in uno studio randomizzato-2*” that will follow 5-day of the FMD meal program every three months, for one year.

Selection and withdrawal of subjects of the previous clinical study

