6.3. Blood Pressure Measurements

Subjects will not consume any caffeine or alcohol or use tobacco products within 6 hours of the blood pressure measurement. Subjects will have their blood pressure on each visit. Subject's blood pressure will be measured in the left arm sitting position three times at 2-minute intervals following the American Heart Association (AHA) guidelines for blood pressure measurement. Heart rate will be measured with each blood pressure measurement.

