6.4. Body Impedance Analysis

The BIA technique is based on the fact that lean tissues have a high water and electrolyte content, and thus provide a good electrical pathway. Fat contains a lower percentage of body water, and thus is a poor conductor of the electrical signal. Utilizing a low energy, high frequency, electrical signal (50 kHz, 500 micro amp), a measurement of the baseline resistance and reactance to the flow of electrical current can be made. The measurement relates directly to the volume of the conductor, which is used to determine total body water, lean body mass, and finally, fat mass and percent body fat measurement on the Tanita® scale.

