8.6. Study conclusions

Collected data from subjects will be reviewed to demonstrate that favourable changes are noted in biomarkers of body composition and age-related biomarkers with administration of the proprietary food products. Data will be evaluated for change from baseline over time within arms and for differences between the intervention arm and the control arm of previous study.

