8.6.1. Analysis supporting primary objectives

Generalized mixed linear models will be used to compare the fat mass percentage change between the value measured at the end of the trial vs the baseline value. The analysis will include a fixed term modeling the change of fat mass between baseline and the second follow-up visit (after 1 year), as well as a random term accounting for repeated measurements on the

same participants. We hypothesize that the coefficient associated with the fixed term (fat mass) will be either equal to zero (no change) or negative (reduction of fat mass).

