8.6.4. Subgroup analyses

To explore the effect of treatment in subgroups, the estimated effect of the nutritional interventions will be estimated for each of the subgroups listed below will be derived. No adjustment for multiple comparisons will be made. Additionally, the frequency and percentage of subjects reaching the primary endpoint will be presented by treatment group for each of the subgroups based on the baseline measurements: baseline fat mass (\geq 20% and \geq 25% for men; \geq 30% and \geq 35% for women), age groups (30-50, 51-70 years), gender, baseline BMI (25-29.9; 30 and over);

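### The primary analysis never tests the 50%-retention endpoint, and the only output that does, a per-subject percentage, is pulled towards 50% by measurement error

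*Protocol*

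**What the plan says.** Section 2.2.1 gives the primary endpoint as "maintenance of at least 50% of the fat mass lost during the previous trial and measured after one follow up year on FMD every 3" (unit: months). It does not say whether the rule applies to each person or to the group, and it sets no minimum loss.

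Section 8.6.1, the analysis for the primary objective, reads "Generalized mixed linear models will be used to compare the fat mass percentage change between the value measured at the end of the trial vs"; its comparator is the baseline value. Its fixed term is the change between baseline and the second follow-up visit. Sections 3.1.1 and 3.2 say that assessments at entry serve as the baseline of the new study. The stated expectation is "We hypothesize that the coefficient associated with the fixed term (fat mass) will be either equal to zero (no change"; the sentence then also allows a negative value.

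Section 8.6.4 adds that "the frequency and percentage of subjects reaching the primary endpoint will be presented by treatment group" for each subgroup. This needs a yes/no classification of every subject, and no proportion is named as evidence of maintenance. Section 8.6 also plans in general terms to look "for differences between the intervention arm and the control arm of previous study", without linking this to the 50% rule.

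Fat mass comes from BIA, giving "fat mass and percent body fat measurement on the Tanita® scale" (section 6.4). No replicate rule is stated for it. Blood pressure, by contrast, is "measured in the left arm sitting position three times at 2-minute intervals" (section 6.3).

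**The concern.** The endpoint concerns how much of an earlier loss is kept, so it needs three fat mass values: parent start, parent end and month 12. The model in 8.6.1 uses none from the parent trial. A group that regained everything before entering this study and then stayed level would show a coefficient of zero, as hypothesised, yet fail the endpoint. A group that lost 2 kg in the parent trial and regained 0.5 kg after the new baseline would show a positive coefficient, yet keep 1.5/2 = 75% of its loss.

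That leaves the percentage in 8.6.4 to carry the endpoint. Dichotomising noisy readings at half of a possibly small loss moves that percentage towards 50%. A result near 50% could mean that nobody changed, that everyone kept about half, or that half kept all and half kept nothing. It cannot be read directly as the share of participants who kept their benefit.

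**Working it through.** **The rule.** Let B and E be measured fat mass at the start and end of the parent trial, and F at month 12. Keeping at least half means B − F ≥ 0.5 × (B − E), which rearranges to

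D = (B + E)/2 − F ≥ 0.

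**Inputs.** The 50% threshold is from 2.2.1. The protocol gives neither the true loss L nor the within-person SD s of a BIA value, so both are assumptions. Errors are taken as normal, independent and of equal SD.

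**Error in D.** Its variance is s² × (1/4 + 1/4 + 1) = 1.5 s², so its SD is s√1.5. The covariance of (B + E)/2 with the measured loss B − E is (s² − s²)/2 = 0, because errors are equal and independent.

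**No true change.** D is then centred on 0 and independent of the measured loss. The rule fires in 50% of measured losers, whatever minimum measured loss is required. A simulation of 2,000,000 persons gives 50.0% for any measured loss and 49.8% to 50.0% for minimum losses of 0.5 to 2 SD.

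**True loss L, the same for everyone.** The true value of D is −L/2 after complete regain and +L/2 after complete maintenance. Hence

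P(scored maintained) = Φ(−L / (2s√1.5)) or Φ(+L / (2s√1.5)).

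| Assumed L/s | L / (2s√1.5) | Complete regain scored maintained | Complete maintenance scored maintained |
|---|---|---|---|
| 1 | 0.41 | 34% | 66% |
| 2 | 0.82 | 21% | 79% |
| 3 | 1.22 | 11% | 89% |
| 4 | 1.63 | 5% | 95% |

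In kilograms, a 2 kg loss with an SD of 1.5 kg gives 29% versus 71%. Over assumed losses of 0.5 to 3 kg and SDs of 0.5 to 2 kg, complete regain is scored as maintained in 0.7% to 45.9%.

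**Does a minimum measured loss help?** Not if true change is nil. If true losses vary, it helps in part. With true losses distributed as N(2, 2) kg (mean 2, SD 2) and s = 1.5 kg, complete regain is scored as maintained in about 32% without selection, 26% with a measured loss above 0, 24% above 1 kg and 20% above 3 kg.

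**Mean D instead.** Under the same N(2, 2) kg and 1.5 kg assumptions, mean D is −1.0, 0.0 and +1.0 kg for 0%, 50% and 100% retention. Under exactly 50% retention it stays at 0 after restricting to measured losers. At full maintenance the SD of D is √(1.5 × 1.5² + 1²) = 2.09 kg; the second term is half the SD of true loss. With 267 subjects less an assumed 20% (214), the standard error is 2.09/√214 = 0.14 kg, so a mean of +1.0 kg lies about 7 standard errors above zero.

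**The case against.** The strongest reply is that the stated primary analysis is already a group-level model, and that the per-subject percentage appears only as a descriptive addition under subgroup analyses. A success proportion for a responder rate is also commonly left to a statistical analysis plan, which is not shown. This stands as far as it goes, and the absence of a success proportion is not by itself the finding. It does not repair the mismatch: the group-level model that the protocol fixes answers a different question from its primary endpoint. The comparison with the earlier control arm in 8.6 is not tied to the 50% rule either.

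A reader might go further and infer three things that the document does not support:

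- **That noise makes half of all measured losers count as maintained.** This needs zero true change. Section 1.2 reports preliminary benefits on body composition, and section 3.2 recruits those who achieved the earlier objectives, so zero change for everyone is a reference case and not the expected one.
- **That complete regain cannot be told from complete maintenance.** For one person this depends on L/s. At a ratio of 4 the split is 5% versus 95%. For a group, 214 completers give a 95% half-width of 1.96 × √(0.25/214) = 6.7 percentage points, so 34% and 66% would separate if a reference value existed.
- **That each BIA value is a single reading.** The protocol is silent on replicates, and the parent trial's procedure is not described here.

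Nor does anything show that parent-trial losses differ between the planned subgroups, so distorted subgroup differences are possible but not established.

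**Conclusion.** The concern holds in this limited form. That 8.6.1 does not address the endpoint in 2.2.1 follows from the text and needs no assumption. The pull of the 8.6.4 percentage towards 50% follows from the algebra under equal, independent errors. Its size is not known, because the protocol gives neither the fat loss nor the BIA SD. It is serious at a loss-to-SD ratio of about 2 or less and small at about 4 or more. The 50% figure itself applies only when there is no true change. The change is worth making because the primary endpoint otherwise has no analysis that tests it.

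**What to change.** In 8.6.1, compute for each participant D = (fat mass at parent start + fat mass at parent end)/2 − fat mass at month 12. Estimate mean D in the repeated-measures model, and conclude maintenance only if the lower 95% confidence bound exceeds 0, meaning that on average more than half of the loss was kept. Report the mean retained fraction, (mean B − mean F)/(mean B − mean E), with a bootstrap or Fieller interval. State in 2.2.1 that the 50% criterion is judged in this way. Keep the individual percentage in 8.6.4 as descriptive, with a note that about 50% of measured losers are expected to meet the rule from measurement error alone when there is no true change.

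The cost is wording in 2.2.1, 8.6.1 and 8.6.4. The only data needed are the parent-trial fat mass values that the endpoint already requires. The downside is that the headline becomes a mean contrast in kilograms and not a responder rate.

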3.1.1. Inclusion Criteria

Individuals already included in the aforementioned previous studies *who were assigned to one of the 2 intervention arms: Fasting mimicking diet or fasting mimicking diet plus Longevity diet* and who completed the study less than 6 months prior to starting the new study. Blood tests and a nutritional assessment will be conducted, serving as the baseline for the new study.

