- Any sound medical, psychiatric and/or social reason which, in the opinion of the PI, would preclude safe participation in this study or interfere with compliance.
- Abnormal laboratory findings including: abnormal blood counts (haematocrit < 33% or > 47%; WBC < 3.0 or > 12.0 $\times 10^3/\text{mm}^3$; platelets < 140 or > 500 $\times 10^9/\text{L}$); abnormal kidney function test (creatinine > 2.5 mg/dL) or liver function test(s) (AST, ALT, alkaline phosphatase) > 1.5X the upper limit of normal; serum calcium > 11 mg/dL; serum K < 3.5 mEq/L; Na < 134 or > 148 mmolL⁻¹

3.1.8. *Women of Childbearing Potential*

Contraception: the effects of the study products on the developing human fetus have not been studied extensively. For this reason, women of childbearing potential must agree to use adequate contraception (hormonal or barrier method of birth control; abstinence) prior to study entry and for the duration of study participation. Females of childbearing potential will have a pregnancy test prior to receiving study products. Should a woman become pregnant or suspect she is pregnant while participating in this study, she should inform study staff and her primary care physician immediately.

Pregnancy: because there is an unknown but potential risk for adverse events in pregnant women during treatment with the study products, pregnant women are not eligible for study participation.

Breast-feeding: Because there is an unknown but potential risk for adverse events in nursing infants secondary to treatment of the mother with the study products, breastfeeding mothers are not eligible for study participation.

3.2. *Recruitment*

The participants will be identified within the intervention groups of the previous clinical studies (*Studio degli effetti della dieta mima-digiuno e della dieta della longevità sulla composizione corporea, fattori di rischio per malattie età-correlate e marcatori dell'invecchiamento in uno studio randomizzato 1 and 2*) who are willing to start a new study for other 12 months, and who completed the study less than 6 months prior to starting the new study and achieved the study's objectives. Blood tests and a nutritional assessment will be conducted, serving as the baseline for the new study. The recruitment period will last up to 3 years

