8.6.2. Analysis supporting secondary objectives

We will also evaluate the effect of FMD on risk factors for CVD and metabolic syndrome, defined as three of five of the following conditions: abdominal obesity, elevated fasting glucose, elevated blood pressure, high serum triglycerides, and low HDL cholesterol.

We will select clinically relevant cutoffs and compared normal and at-risk subjects for each risk factor: total cholesterol >199 mg/dl and LDL cholesterol levels >130 mg/dl are associated with an increased risk for CVD, a fasting glucose >99 mg/dl indicates impaired fasting glucose/prediabetes, and triglyceride levels >100 mg/dl as well as CRP >1 mg/liter are associated with increased risk for CVD. For serum IGF-1, no clinically relevant risk level has been established, but a number of epidemiological studies have associated IGF-1 levels above 200 ng/ml with various cancers (Levine et al., 2014; Pollack et al., 2007). We will therefore compare the effect of FMD cycles on subjects in the highest quartile of IGF-1 expression (>225 ng/ml) with that on subjects with IGF-1 levels \leq 225 ng/ml. The effect of FMD and FMD+LD treatments on these risk factors will be assessed also stratifying our sample by baseline BMI, SBP and DBP, fasting glucose, cholesterol, CRP and IGF-1.

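### Section 2.2.2 lets the secondary endpoint be met by half-retention of any one of nine overlapping risk-factor gains, although 2.1 makes each factor its own maintenance objective

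*Protocol*

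**What the plan says.** Protocol 2.2.2 words the secondary endpoint as "maintenance of at least 50% of one or more risk factors improvements achieved during the previous clinical trial", measured after one year. It then names nine measures: body mass, BMI, blood pressure, IGF-1, HbA1c, fasting glucose, LDL, total cholesterol and CRP. Medication use follows in a separate sentence and is not one of the nine.

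The secondary objectives in 2.1 cover the same measures, but as a plain list: "maintenance of body weight, body mass index, blood pressure, IGF-1, haemoglobin A1c, fasting glucose", followed by the lipids and CRP. Nothing there says that one of them is enough.

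Section 8.6.2 works factor by factor, with cut-offs and with strata ("stratifying our sample by baseline BMI, SBP and DBP, fasting glucose, cholesterol, CRP and IGF-1"). Section 8.6 describes the general approach: "Data will be evaluated for change from baseline over time within arms". Neither section returns to the words *one or more*.

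**The concern.** The endpoint is weaker than the objective it serves. Under 2.1, the diet should maintain each listed factor. Under the literal text of 2.2.2, it succeeds if half of one gain survives, whatever happens to the rest. A follow-up year in which most of the parent-trial gains are lost could then be reported as having met the secondary endpoint.

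The list also counts some information twice. Adult height is fixed, so half-retention of body mass is half-retention of BMI. LDL is a component of total cholesterol. Nine entries are therefore fewer than nine separate chances to show a lasting effect, and the wording does not recognise this.

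**Working it through.** **The text alone.**

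1. Section 2.2.2 lists 9 factors and requires at least 1. One kept and eight lost satisfies it.
2. That pattern cannot arise through body mass or BMI, because the two are kept or lost together. It can arise through CRP or IGF-1, for example.
3. Section 2.1 has no counterpart to the words *one or more*. No other section limits or withdraws them.

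**Illustration of size.** The protocol gives no SDs or correlations for these factors, so those below are assumptions.

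*Sample size.* Section 8.1 gives a maximum of 267. With two intervention arms of 167 (section 1.2) and 20% loss, 334 × 0.80 = 267.2. With the stated 21% and 18%, 167 × 0.79 + 167 × 0.82 = 268.9. The stated figure is reproduced closely enough, and n = 267 is used.

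*Rule on group means.* Let P0 and P1 be the start and end of the parent trial and T2 the one-year value, with lower values favourable. A factor counts as kept if P1 < P0 and T2 ≤ (P0 + P1)/2.

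*Assumptions.* Visit errors are independent with SD 1. The true gain is g = 0.25 SD. Tau, the between-participant SD of the true retention contrast, runs from 0 to 1. Correlations are 0.98 (body mass–BMI), 0.9 (LDL–total cholesterol), 0.4 (glucose–HbA1c) and 0.3 elsewhere.

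*Standard errors.*
- Gain P1 − P0: √(2/267) = 0.0865. The chance of an observed gain is Φ(0.25/0.0865) = Φ(2.89) = 0.998.
- Contrast T2 − (P0 + P1)/2: √((1.5 + tau²)/267), which is 0.0750 at tau = 0 and 0.0968 at tau = 1.

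Under these errors the gain and the contrast are uncorrelated, so their probabilities multiply.

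*One factor.* The true contrast lies g/2 = 0.125 from the 50% line, on the favourable side if the gain is kept and on the other side if it is lost.
- Kept: 0.998 × Φ(1.67) = 0.950 at tau = 0; 0.998 × Φ(1.29) = 0.900 at tau = 1.
- Lost: 0.998 × Φ(−1.67) = 0.048 at tau = 0; 0.998 × Φ(−1.29) = 0.098 at tau = 1.

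*Nine factors, rule of one or more (simulation with the correlations above).*

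| Truth | Gain | tau = 0 | tau = 1 |
|---|---|---|---|
| One kept, eight lost | 0.25 SD | 95% | 92% |
| All nine lost | 0.25 SD | 25% | 42% |
| One kept, eight lost | 0.5 SD | 99.96% | 99.5% |
| All nine lost | 0.5 SD | 0.3% | 3.4% |

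If the nine were independent, the all-lost chance at 0.25 SD would be 1 − (1 − 0.048)⁹ ≈ 0.36 at tau = 0 and 1 − (1 − 0.098)⁹ ≈ 0.60 at tau = 1. Overlap lowers the chance but does not remove it.

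At 0.5 SD, noise alone rarely meets the rule. The lasting fault is that one factor stands in for nine.

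**The case against.** The best defence is that separate endpoints were meant. The heading of 2.2.2 is plural, 2.1 lists each factor, and 8.6.2 compares participants factor by factor. This stands as a possible reading. It does not settle the matter, because the operative sentence still says *one or more*. If separate endpoints were meant, deleting those words changes nothing in the intent.

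It can also be said that the 92–95% nearly restates the premise: if one kept factor suffices, one kept factor usually passes. That is fair. At tau = 0 the kept factor alone gives 0.950. The figures only illustrate the rule, and the case rests on the wording.

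A third defence is that the method for judging 50% retention belongs in a statistical analysis plan. That also stands, and its absence from 8.6.2 is not criticised here. The endpoint definition, however, is fixed in the protocol, and an analysis plan could only carry it out or contradict it.

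Three stronger readings are tempting, but the protocol does not support them:

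- *That the wording drives the interim efficacy conclusion in 8.7.* That look is at six months, while the endpoint is at one year. Table 1 schedules haematological analyses only at baseline and the second follow-up visit, so six of the nine factors (IGF-1, HbA1c, glucose, LDL, total cholesterol, CRP) have no scheduled six-month value. Section 8.7 sets no success rule on *one or more*.
- *That most participants would count as responders through visit-to-visit noise.* This needs a per-participant rule. The only responder count is in 8.6.4, where "the frequency and percentage of subjects reaching the primary endpoint will be presented by treatment group", and that is the primary endpoint.
- *That readers could not see which gains were lost.* Nothing says individual results would be withheld, and 2.1 and 8.6.2 treat the factors individually.

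**Conclusion.** The point holds as a fault in the endpoint definition. Section 2.2.2 as written accepts half-retention of one listed gain, which does not match the objectives in 2.1, and no passage corrects it. At best the wording is ambiguous; at worst it allows maintenance to be claimed when most gains are gone. It concerns a secondary endpoint and is cheap to repair, so it should be fixed but does not threaten the trial.

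The textual conclusion needs no assumptions. The illustrative 92–95% (one kept) and 25–42% (all lost) depend on n = 267, gains of 0.25 SD, equal independent visit error, background correlation 0.3, and tau from 0 to 1. Other values would move them, as the 0.5 SD rows show.

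**What to change.** - Delete *one or more* from 2.2.2.
- Make at least 50% retention of each listed factor its own secondary endpoint, in line with 2.1. Count body mass and BMI as one, and take SBP and DBP separately as 8.6.2 does. This gives 9 − 1 + 1 = 9 endpoints.
- Report each factor's retention with a 95% interval, whether the gain was kept or lost.
- If multiplicity is not adjusted, label these results descriptive. With nine independent factors each exactly at 50% retention, the chance that at least one interval lies wholly on the favourable side is 1 − 0.975⁹ = 0.204. Overlap lowers this.

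No new data are needed, because the endpoint as worded already requires the parent-trial start and end values and the one-year value. The cost is that a single retained factor can no longer support an overall secondary maintenance claim. Small gains will also often give an inconclusive interval: at n = 267, a fully kept gain of 0.25 SD puts the whole interval beyond the 50% line with probability Φ(0.125/SE − 1.96), which is 0.25 at tau = 1 and 0.39 at tau = 0.

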3.1.3. Prohibited Medications, Medical Foods or Nutritional Supplements

- Change in prescription medications, over-the-counter (OTC) medications, medical foods, and nutritional supplements within 30 days prior to the start and for the duration of the study.
- Use of medications classified as narcotics 15 days prior start and for the duration of the study.
 - Use of prescription medications and/or over-the-counter medications for acute and semi-acute medical conditions 15 days prior to start and for the duration of the study. Use of acetaminophen is permitted on an as-needed basis.
 - Use of an investigational drug or participation in an investigational study within 30 days prior to the start and for the duration of the study.
 - Use of anticoagulant medications (heparin compounds or warfarin) within 30 days prior to the start and for the duration of the study. Use of aspirin 400 mg once daily is permitted
 - Subjects will not be allowed to discontinue prohibited prescription medications to meet enrolment criteria.

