During the first follow-up visit, the study staff will assess the signs and symptoms of adverse events and review compliance to the FMD program. The visit will also include body composition assessment using BIA, measurement of height, weight, and vital signs, medical history and current medications. Participants will receive the FMD boxes for the remaining two cycles together with the ketone test strips for self-monitoring of urinary ketone bodies during the FMD cycles.

Follow-up visit 2

During the second follow-up visit, the study staff will assess the signs and symptoms of adverse events and review compliance to the FMD program. This visit will also include body composition assessment using BIA, measurement of height, weight, and vital signs, medical history and current medications. In addition, a collection of fasting blood for haematological and for the genetic analyses will be performed.

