4.2. Prohibited Medications and Procedures

No concomitant prescription medications, over-the-counter medications, medical foods, and nutritional supplements are to be started, or doses changed during the study unless they are prescribed by the subject's primary care giver for treatment of a specific clinical event.

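### The risk-factor maintenance endpoint in 2.2.2 sets no medication condition, so an improvement that was lost and then treated with a drug can be counted as maintained under FMD

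*Protocol*

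**What the plan says.** Section 2.2.2 defines the secondary endpoint as "maintenance of at least 50% of one or more risk factors improvements achieved during the previous clinical trial", assessed after a year of three-monthly FMD cycles. The factors are "body mass, body mass index, blood pressure, IGF-1, haemoglobin A1c, fasting glucose, LDL, total cholesterol, and C-Reactive Protein". The same item adds a drug-use outcome: "Determine long-term trends in the reduction/stabilization in the use of antihypertensive and glucose-lowering drugs or other commonly used medications".

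Three other places bear on medication:

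- Section 3.1.3 lists medication changes among its prohibitions, up to the end of follow-up: "Change in prescription medications, over-the-counter (OTC) medications, medical foods, and nutritional supplements within 30 days prior to the start and for the duration of the" [...]. It states no exception for changes of this kind.
- Section 4.2 also bars new drugs and dose changes, but exempts those prescribed by the participant's "primary care giver for treatment of a specific clinical event".
- Section 8.6.2 gives cutoffs and baseline strata for the risk factors. Medication is not among the strata, and changes in medication are not mentioned.

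For data collection, Table 1 ticks Medications at screening, baseline and follow-up visit 2, and leaves follow-up visit 1 blank. The text for follow-up visit 1 nevertheless includes "measurement of height, weight, and vital signs, medical history and current medications".

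**The concern.** Blood pressure, fasting glucose, HbA1c, LDL and total cholesterol all respond to drugs in common use. The endpoint asks whether at least half of the earlier improvement is still present at one year, without asking what is holding the value there. If the improvement has gone and a drug then brings the value back, the definition as written lets that participant be counted as a success of the diet.

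Such changes are plausible in this population. Section 3.1.4 admits systolic pressure up to 200 mmHg, 3.1.2 admits metformin users, and follow-up lasts 12 months. The error also has a direction: treatment tends to be started in people whose values have worsened, so the maintenance rates are pushed upwards.

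Section 2.1 states the aim as the long-term effect of the FMD plan on keeping these improvements. There is no concurrent control arm in which background treatment would act in the same way. The comparison in 8.6 is with the control group of the earlier trial, which section 1.2 describes as covering a 6-month period.

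**Working it through.** **1. The protocol's own figure.** The only sample-size number is the maximum of 267 in 8.1. With 167 per intervention arm (1.2) and drop-out of 21% and 18% (8.1):

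- FMD: 167 × (1 − 0.21) = 131.93
- FMD+LD: 167 × (1 − 0.18) = 136.94
- Sum = 268.87; rounding each arm down, 131 + 136 = 267.

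The figure is reproduced. It allows for drop-out in the parent trials only, so it is a ceiling for this study too.

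**2. What the sections fix together.** Section 2.2.2 gives a 50% rule with no medication condition. Section 4.2 permits starts and dose changes for a clinical event. Section 8.6.2 has no rule for such changes. Section 3.1.3 prohibits them, but no section says that values after a change are excluded or counted as failures. A treated relapse can therefore enter the maintenance rate as a success.

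**3. One participant (assumed values; the protocol gives none).** Systolic pressure fell from 140 to 130 mmHg in the parent trial.

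- Threshold for maintained: 140 − 0.5 × (140 − 130) = 135 or lower.
- Complete relapse, no drug: 140, not maintained.
- Complete relapse, then a drug effect of 5 to 10 mmHg: 135 to 130, maintained, although none of the improvement remains.

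In general, after a complete relapse the status flips once the drug effect reaches half of the earlier improvement. For assumed improvements of 4, 6 and 8 mmHg, that is 2, 3 and 4 mmHg.

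**4. Upper bound for one factor (start rate assumed).**

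- 5% start or intensify: 0.05 × 267 = 13.35, about 13
- 10% start or intensify: 0.10 × 267 = 26.7, about 27

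As a share of 267 this is 5 to 10 percentage points. It is reached only if every such participant had improved in the parent trial, had since lost more than half of that improvement, and was brought back over the threshold by the drug.

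**5. A less extreme illustration.** A simulation gave every participant the 10 mmHg improvement of step 3, a mean regain of 4 to 7 mmHg with SD 8 to 12, and a drug effect of 5 to 10 mmHg. All starters were taken from those who had truly lost the improvement. The number flipped to maintained, out of 267, was:

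| Assumed start rate | Participants flipped | Percentage points |
|---|---|---|
| 5% | 3.9 to 10.8 | 1.5 to 4.0 |
| 10% | 7.8 to 21.8 | 2.9 to 8.2 |

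All of these inputs are assumptions. The table shows that the realised effect lies below the bound in step 4.

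**6. The time window.** The improvement is dated to the end of the parent trial, not to baseline. Section 3.1.1 allows up to 6 months between the two (the screening text under 3.3 says three). The no-change period before the start in 3.1.3 covers 30 days. A drug started earlier in that gap would produce the same false success, and a rule that looks only after baseline would miss it.

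**The case against.** **This may belong in the statistical analysis plan.** Handling of medication changes is often left to that document, which is not shown, and 2.2.2 is silent rather than stating that only the measured value counts. Reporting values regardless of treatment is also a legitimate strategy if it is declared. This stands in part: the protocol does not declare a value-only rule, and a later document could add one. But the endpoint is defined in 2.2.2, the protocol has its own analysis section, and neither restricts what counts as maintained. A regardless-of-treatment rate would also not answer the aim in 2.1 on its own.

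**Section 3.1.3 already prohibits the changes.** It does, and it conflicts with 4.2 and with a drug-use outcome that expects use to vary. The prohibition does not remove the problem, because the protocol attaches no analytic consequence to a change that occurs.

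**The size is assumed.** This is correct. In addition, 267 is a maximum, participants with no parent-trial improvement in a factor cannot be classified for it, and if the phrase about one or more factors is read as a composite, one drug-affected factor need not change a participant's status.

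**A stronger reading that the text does not carry.** A reader might infer that the two parts of 2.2.2 contradict each other, with a drug reduction scoring as a benefit on one and a failure on the other. A reduction can indeed raise the value: a pressure of 132 held on a drug, with an assumed rise of 5 to 10 mmHg, would read 137 to 142 against the threshold of 135. But the drug-use item is a descriptive trend with no per-person score, and lowering a drug because values have improved does not clearly fit the exception in 4.2.

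**Conclusion.** The point holds for starts and increases. As written, 2.2.2 and 8.6.2 allow a blood-pressure, glucose, HbA1c or lipid improvement that was lost and then treated to count as maintained under FMD. The bias is upwards, and the design has no concurrent control to expose it. It concerns secondary endpoints.

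The size cannot be derived from the protocol. On an assumed 5-10% of at most 267 participants starting or intensifying a relevant drug, 13-27 participants is an upper bound for a single factor, not an estimate. Whether a given participant flips depends on the size of the drug effect and of the regain.

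The Table 1 discrepancy is minor for the one-year endpoint, because Medications is ticked at follow-up visit 2. It matters somewhat more for the 6-month interim analysis in 8.7, since blood pressure is measured at follow-up visit 1.

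**What to change.** - In 2.2.2 and 8.6.2, state that a participant who starts or increases a drug acting on a factor after the end-of-parent-trial measurement counts as not having maintained that factor. Report the value-only rate as a sensitivity analysis.
- For drug reductions, keep the value-based status and cross-tabulate it with the reduction. Do not reclassify it as a success; excusing every reduction would tilt the rates in favour of the diet.
- Reconcile 3.1.3, 4.2 and the drug-use outcome in 2.2.2. Which medication rule applies is for the investigators to settle.
- Align the Medications row of Table 1 with the text for follow-up visit 1.

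The cost is wording and one table entry. Current medication is already recorded in this study. The window also needs each participant's medication at the end of the parent trial, from that trial's records or by asking at screening. The downside is slightly lower maintenance rates.
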